Secondary Obective:

To evaluate effect of fluoxetine on HCVR and peri-ictal respiratory

depression in drug resistant epilepsy patients.

Version 01.2 Protocol:201607761 Version 01.2

Endpoint Primary End point:

Study recruitment rate assessed every 3 months through the study

completion

Study retention rate assessed every 3 months through the study completion

Secondary End point:

Change in mood score using PHQ-9 score

Change in minute ventilation during HCVR testing

Change in slope of HCVR

Difference in duration of abnormal breathing in periocal period

Difference in oxygen saturation during periotal period

Difference in CO₂ level in periotal period

Exploratory End points: Change in VRTCO₂

Change in time to VRTCO₂

Change in time to end of HCVR testing

Population: Subjects age 18-75 years, both genders, drug resistant epilepsy with no

prior severe depression or other psychiatry co-morbidities but otherwise healthy, mostly living in State of Iowa will be screened for this study.

Phase: 2 Number of Sites 1

enrolling participants:

[figure not shown]
Description of Study Fluoxetine, given by mouth with a standard titration over 6 weeks.

Agent: 10 mg for 1 week, 20 mg for 1 week, 40 mg for 2 weeks, 20 mg for 1 week,

10 mg for 1 week then STOP

Study Duration: 2 years **Participant Duration:** 6 weeks

Version 01.2 Protocol:201607761 06/28/2017

Version 01.2 Protocol:201607761 06/28/2017

I KEY ROLES

[name]

Role: Principal investigator

Institution: The University of Iowa,

Address: [name]

[contact] Email: [contact]

[name] Role: Co-Investigator

Institution: The University of Iowa,

Address: [name]

[contact] Email: [contact]

[name] Role: Co-Investigator

Institution: The University of Iowa,

Address: [name]

[contact] Email: [contact]

[name] PhD

Role: Co-Investigator

Institution: The University of Iowa,

Address: [name]

[contact]

Email: [contact]

[name] [name] Role: Biostatistician

Institution: The University of Iowa,

Address: [name]

[contact] Email: [contact]

[name] PhD

Role: Independent Medical Examiner Institution: The University of Iowa,

Address: [name]

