• 2) To test effect of fluoxetine on peri-ictal respiratory depression: Subjects will be screened in neurlogy clinic from a group of previously diagnosed patients with epilepsy who are planned for VEEG study. Eligible subjects will undergo HCVR testing. Eligible subjects with a reduced baseline HCVR slope (<2.0 L/min/mmHg) will be enrolled and randomized to fluoxetine vs placebo (1:1) until a total of 20 subjects complete the study. Both the subjects and investigators will be blinded to the randomization process. A standard titration plan for fluoxetine & placebo will be as above, for 4 weeks prior to EMU admission. During EMU admission, the subjects will be monitored with VEEG, EKG, EMG, SpO₂, tcCO₂/ETCO₂, oral & nasal thermistor & pressure transducer to measure airway pressure, and RIP with abdominal & chest belts to measure change in circumference during respiration. Peri-ictal respiratory changes in the two groups will be compared to assess the effect of fluoxetine.

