6.1.7 STARTING DOSE AND DOSE ESCALATION SCHEDULE

10 mg once a day for one week, 20 mg once a day for one week, 40 mg once a day for two weeks, 20 mg once a day for one week and 10 mg once a day for one week. Then STOP.

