6.1.8 DOSE ADJUSTMENTS/MODIFICATIONS/DELAYS

Subjects will be allowed to take 40 mg/day of drug vs placebo for maximum of an extra 1 week in case of delay in follow up appointment.

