7.3.2 ENROLLMENT/BASELINE

- Obtain informed consent of potential participant verified by signature on study informed consent form
- Verify inclusion/exclusion criteria.
- Obtain urine pregnancy test when applicable.
- Obtain demographic information, medical history, medication history, alcohol and tobacco use history.

Version 01.2 Protocol:201607761 Version 201.2

- Perform HCVR testing
- PHQ-9 score
- Randomize to one of the intervention arm
- Discharge randomized subjects with assigned treatment with one week of 10 mg, one week of 20 mg and 4 weeks of 40 mg pills.

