7.3.3 FOLLOW-UP

Follow up phone call at end of week 1 and 3

Record for adverse events as reported by the participants.

If suspicious for mania, will perform full Altman self-report maniac scale

Record compliance to assigned treatment as reported by the participants.

Record current medication

Follow up visit 4 weeks (+/-1 week) after randomization

Record for adverse events as reported by the participants.

Record compliance to assigned treatment as reported by the participants and by counting pill from the pill container brought by the participants.

Record PHQ-9 score

Repeat HCVR testing

Record current medication

Video EEG study with comprehensive respiratory monitoring in EMU for paticipants enrolled at neurology clinic

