10.6 MEASURES TO MINIMIZE BIAS

10.6.1 ENROLLMENT/ RANDOMIZATION/ MASKING PROCEDURES

Subjects will be screened and enrolled in two locations, neurology clinic and EMU. A total of 20 subject will be enrolled in each location and they will be randomized to drug vs placebo group equally (1:1) using computer generated random numbers. The assignment for each subject will be kept in a sealed envelope and will be provided to investigational drug pharmacy at the University of Iowa.

The participants as well as the investigators (except one) will be blinded to the drug the participant is receiving. Bottles of the study drug will be labelled with the name of study, drug A or drug B, and instruction of titration plan.

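### The dispensing list in section 7.3.2 contradicts the dosing schedule in section 6.1.7 and contains no capsules for the taper

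*Combined protocol and SAP*

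**What the plan says.** **Dosing.** Section 6.1.7 steps up from 10 mg to 20 mg at weekly intervals, holds 40 mg for two weeks, and then steps down: "20 mg once a day for one week and 10 mg once a day for one week. Then STOP". The protocol summary gives the same sequence, including "20 mg for 1 week, 40 mg for 2 weeks, 20 mg for 1 week". Section 6.1.5 sets once-daily dosing and section 6.1.9 a duration of six weeks. Section 6.1.8 allows 40 mg "for maximum of an extra 1 week in case of delay in follow up appointment".

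**Dispensing.** The enrollment steps in section 7.3.2 read: "Discharge randomized subjects with assigned treatment with one week of 10 mg, one week of 20 mg and 4 weeks of 40 mg pills". They make no distinction between EMU and clinic participants.

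**Later contacts.** Section 7.3.3 has a "Follow up visit 4 weeks (+/-1 week) after randomization", at which compliance is checked from participants' reports and "by counting pill from the pill container brought by the participants". It lists no dispensing. Section 7.3.4 is a telephone call at week 7.

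**Labelling.** Section 10.6.1 says: "Bottles of the study drug will be labelled with the name of study, drug A or drug B, and instruction of titration plan". It does not say what that instruction contains.

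**EMU timing.** For clinic participants, section 4.1 part 2 says: "A standard titration plan for fluoxetine & placebo will be as above, for 4 weeks prior to EMU admission". Section 7.3.3 lists their EMU recording under the week-4 visit.

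**The concern.** The two sections cannot both be carried out. By the end of week 2 the dispensed 10 mg and 20 mg capsules are used up, and only 40 mg capsules remain. A participant who takes them as supplied stays at 40 mg for two weeks longer than the schedule allows and then stops abruptly.

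This is first a safety matter. Section 2.3.1 lists serious symptoms from sudden discontinuation of fluoxetine, and section 7.4 justifies the titration partly by the need to limit withdrawal effects. It also leaves unclear which exposure the trial tested after week 4.

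A smaller question arises only if section 6.1.7 is followed. Step-down then begins after four weeks, about when clinic participants enter the EMU, and no text says whether it waits for the recording to finish.

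**Working it through.** **Inputs.** Schedule from section 6.1.7 and the summary; supply from section 7.3.2; once-daily dosing from section 6.1.5; extra week from section 6.1.8. Day 1 is the first dose, and a week is 7 daily doses.

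**Stated duration.** Section 6.1.7: 1 + 1 + 2 + 1 + 1 = 6 weeks. Section 7.3.2: 1 + 1 + 4 = 6 weeks. Both reproduce the six weeks in section 6.1.9, so the total length does not reveal the conflict.

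**Days of each strength.**

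| Strength | Needed, 6.1.7 | Supplied, 7.3.2 | Supplied minus needed | Needed with 6.1.8 extra week | Supplied minus needed |
|---|---|---|---|---|---|
| 10 mg | 7 + 7 = 14 | 7 | -7 | 14 | -7 |
| 20 mg | 7 + 7 = 14 | 7 | -7 | 14 | -7 |
| 40 mg | 14 | 4 × 7 = 28 | +14 | 14 + 7 = 21 | +7 |
| Total | 42 | 42 | 0 | 49 | -7 |

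All 7 + 7 = 14 taper days lack matching capsules, with or without the extra week.

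**Dose by day.** Days 1 to 28 agree: 10 mg to day 7, 20 mg to day 14, 40 mg to day 28. On days 29 to 42 section 6.1.7 gives 20 mg for 7 days and 10 mg for 7 days, while the dispensed supply gives 40 mg throughout.

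**Total dose in the active arm.**
- Section 6.1.7: 14 × (10 + 20 + 40) = 980 mg.
- Section 7.3.2: 7 × 10 + 7 × 20 + 28 × 40 = 1330 mg, which is 350 mg more.

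**Participants on fluoxetine.** With the 40 planned in the summary at 1:1, 40 × 1/2 = 20.

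**Pill count.** If each daily dose is one capsule (an assumption; the documents do not say), 42 - 28 = 14 capsules remain after day 28 under either list. A total count would not show the error; a count by strength would.

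**Timing if section 6.1.7 is followed.** The last scheduled 40 mg dose is on day 28 and the first 20 mg dose on day 29. The visit window is 28 ± 7, or days 21 to 35. Of these 15 days, 8 (days 21 to 28) fall before step-down and 7 (days 29 to 35) within it, unless the delayed-visit extension is used. The documents give no EMU stay length, so the overlap with recording cannot be sized.

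**Final call.** Take the week-7 call as day 49. The last dose is on day 42, so the call comes 49 - 42 = 7 days later. With the extra week the last dose is on day 42 + 7 = 49, and the call comes 0 days later.

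**The case against.** Section 7.3.2 may be a drafting slip. Section 6.1.7 and the summary agree with each other, and an experienced pharmacy might dispense from them. Staff inspecting the container at a week-4 visit on or before day 28 could see that only 40 mg capsules remain. Taper capsules could also be handed out at that visit. All of this is possible, but none of it is written down, and even then 40 mg would be oversupplied by one to two weeks.

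A reader might infer that the bottle label will tell participants to step down on day 29 with capsules they do not have. The documents do not support this: section 10.6.1 mentions only a titration instruction, and section 4.1 part 1 describes the titration plan as four weeks with no taper.

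A reader might also infer that clinic participants' peri-ictal recording takes place at a reduced dose and that this biases the comparison. That goes too far, for four reasons:
- Whether a nominal four-week admission falls on day 28 or day 29 depends on how days are counted.
- The overlap arises only if section 6.1.7 is followed. Under section 7.3.2 participants would still be at 40 mg, so the missing taper and the EMU overlap are alternatives.
- Both arms keep the same calendar.
- The documents give no dose-response and no stay length.

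The peri-ictal outcomes are secondary, and section 10.4.1 plans description without inferential tests.

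On the final call, section 8.3 already records events until 7 days after participation ends. What remains is that no contact is scheduled after the last dose when the extra week is used in full.

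**Conclusion.** The dispensing contradiction stands and should be corrected. Section 7.3.2 as written is 7 days short of 10 mg, 7 days short of 20 mg and 14 days over on 40 mg. The extra week in section 6.1.8 does not reconcile it. Followed literally, it removes the whole 14-day taper; pharmacologically this affects the fluoxetine arm, about 20 of 40 planned participants. The supply arithmetic rests only on once-daily dosing and seven-day weeks.

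The EMU timing and the final call are secondary clarifications. Under section 6.1.7, recording may run into step-down; the documents do not show that it will, or by how much. No bias in the randomized comparison and no size of effect on the peri-ictal estimates is claimed. The feasibility endpoints' definitions and the sample size do not change.

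**What to change.** **Main change.** Rewrite the dispensing step in section 7.3.2 as 10 mg for one week, 20 mg for one week, 40 mg for two weeks (plus up to one extra week under section 6.1.8), 20 mg for one week and 10 mg for one week. State in section 10.6.1 that the label's instruction includes the taper.

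**Secondary clarifications.**
- In sections 6.1.7 and 6.1.8, say that 40 mg or matching placebo continues after day 28 only until the follow-up HCVR test and, for clinic participants, the EMU recording are complete, to day 35 at the latest, and that step-down starts then. The label must allow for this variable start. Recording that runs past day 35 would still fall in step-down; the scheduled dose can be worked out from the randomization, testing and recording dates.
- In section 6.1.9 and the summary, give the duration as six weeks, up to seven.
- In section 7.3.4, place the final call one week after the last dose: day 49 as a rule, and up to day 49 + 7 = 56 when the extra week is used.

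**Cost.** Short text edits, an IRB-approved amendment (section 12.2) and possibly a consent update (section 12.3.2). Some participants would have up to one more week at 40 mg, no more than section 6.1.8 already permits for a delayed visit, and a later final call.

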7.3.3 FOLLOW-UP

Follow up phone call at end of week 1 and 3

Record for adverse events as reported by the participants.

If suspicious for mania, will perform full Altman self-report maniac scale

Record compliance to assigned treatment as reported by the participants.

Record current medication

Follow up visit 4 weeks (+/-1 week) after randomization

Record for adverse events as reported by the participants.

Record compliance to assigned treatment as reported by the participants and by counting pill from the pill container brought by the participants.

Record PHQ-9 score

Repeat HCVR testing

Record current medication

Video EEG study with comprehensive respiratory monitoring in EMU for paticipants enrolled at neurology clinic

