4 STUDY DESIGN AND ENDPOINTS

4.1 DESCRIPTION OF THE STUDY DESIGN

Double blind placebo-controlled randomized prospective trial

Two enrolling locations: EMU and Neurology Clinic

1) To test effect of Fluoxetine on HCVR: Subjects will be screened in the EMU and neurology clinic. Subjects eligible are those with patients with epilepsy who have a reduced baseline HCVR slope (<2.0 L/min/mmHg). Subjects will be enrolled, and randomized to either fluoxetine or placebo (1:1) until 20 subjects complete the study. Investigational Drug Services (IDS), at the University of Iowa Hospitals and Clinics (UIHC), will be responsible for randomizing and dispensing the

Version 01.2 Protocol:201607761 Version 20.2 Version 01.2

drugs. Both fluoxetine and placebo will be encapsulated in identical casing to mask their identity. Both the subjects and the investigators will be blinded to the randomization process. A standard titration plan will consist of fluoxetine or placebo 10 mg per day for a week, then 20 mg per day for a week and then 40 mg per day for 2 weeks, upon discharge. Subjects will return after 4 weeks for follow up HCVR testing in the Clinical Research Unit at UIHC. For each subject, the magnitude of post-treatment HCVR in terms of HCVR slope, minute ventilation, VRTCO₂, time to VRTCO₂ and time to target ETCO₂ at the end of the study will be compared with their baseline HCVR. The medication adherence rate, safey concerns and change in mood scale will be assessed at follow up. Reported adverse effects will be collected for all subjects. Enrolment rate and study completion rates will also be assessed every 6 months.

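### The only post-treatment HCVR may fall a week early and is timed from randomization, so an in-window test can follow as little as 7 of the planned 14 days at the top dose step

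*Combined protocol and SAP*

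**What the plan says.** Section 7.3.3 defines one clinic visit after treatment starts: "Follow up visit 4 weeks (+/-1 week) after randomization". Its procedures include "Repeat HCVR testing". The final contact in 7.3.4 is a telephone call, so this is the only HCVR on treatment.

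Section 6.1.7 gives the upward steps as "10 mg once a day for one week, 20 mg once a day for one week, 40 mg once a day for two weeks", followed by a step-down. Section 4.1 places start of dosing and test together: "40 mg per day for 2 weeks, upon discharge. Subjects will return after 4 weeks for follow up HCVR testing".

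Section 7.3.2 lists randomization and then, as the next item, "Discharge randomized subjects with assigned treatment with one week of 10 mg, one week of 20 mg and 4 weeks of 40 mg pills". It gives no interval between the two.

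For visit timing, section 6.1.8 allows "40 mg/day of drug vs placebo for maximum of an extra 1 week in case of delay in follow up appointment". No section provides for a visit that comes early. Section 10.3 names a per-protocol analysis and sets no minimum exposure or time at the top step.

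**The concern.** Section 4.1 implies a test after the whole up-titration. Section 7.3.3 accepts the same test when only half of the top step may have been taken. The two sections also use different clocks: 7.3.3 counts from randomization, while 4.1 reads most naturally as counting from discharge, when treatment starts. Any days between randomization and first dose then count toward the four weeks although no study drug is taken.

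HCVR slope and minute ventilation (secondary endpoints) and VRTCO2, time to VRTCO2 and time to end of testing (exploratory endpoints) all depend on this one test. Sections 10.1 and 10.4.1 say that the pilot is meant to yield estimates of centre and spread for later studies. A mean change and SD taken over mixed exposures would describe a looser regimen than the one in 4.1, and the analysis as planned would not show it. A test on day 21 enters as a complete observation, and the models in 10.4.3 carry no exposure term.

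**Working it through.** **Inputs.** Window: day 21 to day 35 from randomization (7.3.3). Lower steps: 7 + 7 = 14 dosing days (6.1.7). Top step: 14 days at 40 mg (4.1, 6.1.7), extendable by up to 7 days for a late visit (6.1.8). Lag from randomization to first dose, L: not stated; 0 is the base case, and up to 7 days is shown as an assumption.

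**Formula.** Days at top step before the test = max(0, visit day − L − 14).

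**The plan's own figure.** Visit day 28 with L = 0: 28 − 0 − 14 = 14 days, which matches the two weeks in 4.1.

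**Across the window.** Days at the top step:

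| Visit day from randomization | L = 0 | L = 3 | L = 5 | L = 7 |
|---|---|---|---|---|
| 21 | 7 | 4 | 2 | 0 |
| 28 | 14 | 11 | 9 | 7 |
| 35 (extra week used where needed) | 21 | 18 | 16 | 14 |

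Only the L = 0 column needs no assumed delay. The other columns show how sensitive the result is to L.

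**Cumulative dose at L = 0.** The lower steps give 7 × 10 + 7 × 20 = 210 mg.
- Day 21: 210 + 7 × 40 = 490 mg.
- Day 28: 210 + 14 × 40 = 770 mg.
- Day 35 with the extra week: 210 + 21 × 40 = 1,050 mg.
- In-window ratio: 1,050 / 490 = 2.1.

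**Effect on the estimates (illustration, under an assumption).** The documents give no relation between exposure and HCVR response. Suppose the response were proportional to days at the top step. A test at 7 of 14 days would then show 7/14 = 0.5 of the response expected at day 28. The Protocol Summary randomizes 40 participants 1:1, or 20 per arm. Each such test would lower the fluoxetine mean by (1/20) × 0.5 = 2.5% of that response. Late tests would push the mean the other way, but early and late tests both add to the spread.

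**What each change would do.** Counting from first dose but keeping one week either side gives 7 to 21 days at the top step whatever L is. Counting from first dose with no test before dosing day 28 gives 14 to 21 days.

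The pill supply in 7.3.2 (four weeks at 40 mg) does not match the step-down in 6.1.7, and the two must be reconciled. This does not affect the sums above, because the first two weeks are the same in both.

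**The case against.** The strongest reply is that this is a feasibility pilot with no hypothesis (10.2), no sample size calculation (10.5) and no inferential tests of its efficacy endpoints (10.4.1). In such a trial a symmetric visit window is ordinary practice. Adherence is followed by telephone at weeks 1 and 3 and by pill count at the visit. A tighter window could also cost completed visits, and completion is a primary endpoint (4.2.1). These points lower the stakes and bear on the cost of a fix. They do not answer the mismatch: pill counts address adherence, and nothing in the plan brings time at the top step into the analysis.

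A second reply also stands in part. Attenuation occurs only if the response grows with exposure between the early and the planned test. Even then, early and late visits could offset each other in the mean, though not in the SD.

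A reader might go further than the documents allow in four ways:

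- **That participants will be tested after 0 to 6 days at the top step.** Every value below 7 needs a lag that is not stated, and 0 needs a 7-day lag together with the earliest allowed visit. Section 7.3.2 lists discharge straight after randomization, which is compatible with no lag. The columns of the schedule table in 7.3.7 are visit labels and do not show monitoring that continues for days after randomization.
- **That the shortfall falls mainly on EMU participants.** The early allowance applies to everyone. Only an unstated lag would single out EMU participants.
- **That the permitted spread in cumulative dose is much wider than 2.1-fold.** This requires pairing a low dose under an assumed lag with a high dose under none.
- **That drug levels at the early test are a known fraction of those at day 28.** The documents give no half-life, and drug level is not HCVR response.

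**Conclusion.** The inconsistency stands on the text alone. Section 7.3.3 permits the single post-treatment HCVR a week before the four-week point in 4.1 and counts from a different event. Without any lag, an early in-window test may have half the planned time at the top step. Delay in the first dose would reduce that further by an unknown amount. The text permits such tests; it does not show that they will occur, since no visit-timing data are given. The consequence for the mean and SD is conditional on an exposure-dependent response. The point is worth correcting because the estimates at risk are the ones the pilot is meant to deliver and the remedy is small. It does not undermine the feasibility objective.

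**What to change.** - In 7.3.3, count the HCVR window from first dose.
- Reconcile its early allowance with the four-week test in 4.1 and the late-only provision in 6.1.8, so that the test does not precede completion of the planned up-titration. Changing the anchor alone does not achieve this.
- Record the first-dose date and the number of days at the top step before each follow-up HCVR.
- In the HCVR tables, report days at the top step by arm and flag tests done before dosing day 28.

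The recording and flagging are worthwhile even if the window stays as it is.

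**Cost.** One sentence in 7.3.3, one date field and one derived variable. If the early allowance is removed, the booking window shrinks from 14 days to 7. That could slightly reduce visit completion, notably for clinic enrollees, whose visit includes an EMU study. It would also raise average time at the top step, because every visit after dosing day 28 would draw on the extension in 6.1.8. The sponsor and investigators should weigh both effects when they reconcile the three sections. No change to the dose steps is proposed.
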